## Summary

Globally, one of the major risk factors for adolescent morbidity is considered Malnutrition. Worldwide adolescent age group 10-19 is increasing and they are at increased risk of malnutrition-related diseases resulting in high morbidity and mortality. Asian countries are suffering from the double burden of malnutrition including Pakistan. The risk factors that contribute to malnutrition in the population include unsafe drinking water, poor sanitary conditions, lack of proper waste disposal facilities, poor health awareness, and poor nutrition and hygiene. However, studies have shown that nutrition education, and water, sanitation, and hygiene (WASH) programs in schools are effective strategies to promote the health status of adolescents (girls and boys). The primary objective of this study is to determine a school-based nutrition and WASH education intervention to improve nutritional status among early adolescents. The randomized control trial (RCT) study design will be chosen for this study. This study will be carried out in Gojra public schools, in Punjab. The study participants will be 6-8 grade school-going adolescents (girls and boys), their mothers/immediate caretakers, and school teachers. The data collection methods that will be used for the study are surveys, focus group discussions (FGDs), and through observation. Anthropometric measurements and specified micronutrient levels of adolescents will be measured at baseline and end line. The intervention will consist of skill-based nutrition and WASH education for the adolescents along with deworming and micronutrient supplementation. Workshops based on nutrition and WASH will be arranged for school teachers. This study will be carried out over one year with two-time data collection (baseline, and end line). Data will be analyzed by using SPSS and transcription. The expected outcome of the study would be that the implementation of identified nutrition and WASH strategy is effective to generalize in the poor nutritional status population in schools. It will show the promising benefit of education and WASH intervention, in reducing the cases of

early adolescent malnutrition. Through the findings of the study, we can bring the revolution at the micro-level targeting the community to modify the curriculum of this age group.

## Introduction

Malnourishment is one of the grave public health issues and a significant cause of high morbidity and mortality among young Pakistani children. Several factors determine the high prevalence of malnutrition, which includes unsafe drinking water, poor sanitary conditions, lack of proper waste disposal facilities, poor health awareness, and poor nutrition and hygiene (Hirani, 2012). According to a report by the World Health Organization (WHO) published in 2017, malnutrition was categorized into three broad groups; “**undernutrition** (wasting, stunting, and underweight), **micronutrient related malnutrition** (deficiency or excess of micronutrients), **overweight, obesity and diet-related non-communicable diseases**” (Dat, 2018). According to another report by WHO, which was based on anthropometry, nutrition was classified as under and over-nutrition. According to this classification, **undernutrition** is divided into thinness, stunting, and underweight, while **overnutrition** is grouped into overweight and obesity. This classification of malnutrition was for children over five and adolescents. (De Onis, 2015).

At present, adolescents constitute the major proportion of all the age groups worldwide and 1.8 billion of the total world population consists of adolescents (between 10-19 years of age). Out of these, approximately 90 percent belong to Low and Middle-Income countries (LMICs) (Patton & Kabir, 201, Christian, 2018). The adolescent population was further divided into early and late adolescent by United Nations, the early adolescents age range between 10–14 years, and the late adolescents age group range between 15– 19 years (Christian, 2018).

In 2015, about 1.2 million adolescent deaths occurred globally (WHO,2017), 26 % of them in the South East Asian Region (WHO,2016). The leading causes of death in early adolescents include diarrheal diseases, intestinal infections and respiratory tract infections, and road traffic accidents (Dick, 2015). Malnutrition is the major contributing factor coupled with other causes of adolescent death (Reiner,2019). Globally, the main nutritional issues affecting

adolescents are undernutrition, anemia, and micronutrient deficiencies (Iron, Vitamin A, Zinc, and iodine,) (Shahid, 2009). Around 1.2 million adolescents in developing countries face serious nutritional challenges (Hossain, 2017 & Akhter, 2013).

According to the 2018 National Nutritional Survey (NNS) in Pakistan, adolescent (10-19 years) boys are more affected than girls in terms of being underweight, and more adolescent girls are overweight compared to their male peers. The prevalence of malnutrition across Pakistan varies from one region to the other. All provinces have different rates of malnutrition, the underweight population in Sindh province is higher as compared to other provinces, while the prevalence of obesity on the other hand is high in Baluchistan and KP provinces of Pakistan along with NMD (newly merged districts). In Punjab province, more adolescent boys are underweight than girls.

Survey also showed that 56.6 % of adolescent girls in Pakistan are anemic (NIPS & ICF 2019).

All over Pakistan, the high prevalence of both underweight and overweight/ obese adolescent populations is a major concern and requires serious attention to addressing all forms of malnutrition-associated disorders. According to a report, micronutrient deficiencies and malnutrition were observed in young women between the ages of 15-19 years and children under five years of age. However, the early adolescent female group and males aged between 10- 19 years were not studied in this group for micronutrient assessment, although this age group is 23 % of Pakistan's total population. The early adolescent group (age 10-14 years) consists of almost 12 % of the total population of Pakistan (NIPS & ICF 2019).

The physical and mental growth and learning abilities of adolescents are influenced by many factors. These factors include the health condition of the adolescents and their perception of their health practices, school environment, socio-economic status of their parents, and nearby facilities of health services. The most important factor influencing the health, mental growth, and

educational performance among adolescents is their nutrition status (Mwaniki, 2014 & Madjdian, 2018). Healthy Nutrition results in better growth and development during infancy and adolescents. However, nutritional requirements keep changing through the period of adolescence (Zulfiqar, 2017). Almost 80 % of adolescent's growth is completed in the early adolescence phase and is associated with emotional, cognitive, and hormonal changes (WHO, 2006). Adolescents attain 50 % of their physical growth during the early adolescent period (Hossen, 2016). Their caloric requirements also reach up to 2000-3000 Kcal per day for males, while for females the requirement is 2000-2500 Kcal along with an increase in protein intake requirement of 1.1-1.2 g/kg/day (Paracha,2019). The dietary requirements of both early as well as late adolescent groups are almost the same as well as macro and micronutrients are concerned (WHO, 2006).

The study conducted in Sialkot in 2013 on three hundred twenty-eight school going adolescences of both genders revealed that the diet and nutritional status were not up to the standards of adequacy for micro nutrients (minerals), and females are more affected than males (Rifat-uz-Zaman, 2013). An increase in physical activity along with deprived eating practices and other issues like menstruation highlight the possible risk factor for adolescent's poor nutrition. The results of the research studies conclude that malnutrition leads to deprived physical and mental development, poor resistance to diseases and poor performance at school (Bhutta, 2011 & Haddad, 2015& Bundy, 2018). In addition, adolescent girls' requirement for iron intake increases due to menstrual blood loss. On the other hand, boys have increased iron intake requirement due to muscle mass accumulation along with an increase intake of calcium as the majority of the skeletal growth taking place in this period (Bundy, 2017).

Iron deficiency and anemia lead to decrease or slow cognitive functioning, lower educational achievement, and lower physical capability. Iodine deficiency causes harmful effects

like neural impairment and culminates in poor educational achievements. For healthy immune system functioning and optimal vision, Vitamin A is important. A low level of Vitamin A can negatively affect physical growth and sexual maturation. Zinc is also vital for attaining maximum growth potential (World Bank, 2003).

Other contributory factors of malnutrition include contaminated water, worm infestation, poor personal hygiene practices, and unsatisfactory sanitary conditions (United States Agency International Development USAID, 2015; WHO, 2004). In adolescents, infectious diseases are one of the causes of malnutrition and according to a report by WHO, 88 % of infectious diseases are a result of poor sanitary conditions and poor hygiene habits coupled with unsafe drinking water (WHO, 2004 & 2008a). Poor sanitary, and hygiene conditions and unsafe drinking water resulted in water borne diseases like diarrhea, which in turn contribute to malnutrition. Along with this, diarrhea contributes to absenteeism among school-going adolescents particularly in Pakistan 34 % of girls compared to 40% of boys 10-14 years are out of school (Centers for diseases control and Prevention, 2014 & GAIN,2018). However, it is evident that wherever sanitation facilities improve, accordingly the enrollment rate of girls in those institutions automatically increased. According to WHO data, due to the availability of sanitation facilities, only 11 % more girls attend school (Njau, 2016).

In addition to UNICEF Report 2008, children with worm infestation showed poor performance in cognitive capabilities, and academic achievements that increase absenteeism from school as compared to their healthy peers (Njau, 2016). The highest burden of worm infestation in young school children aged 5-15 years due to poor sanitation and hygiene (Luong, 2003). Study conducted by WHO in Asia and Africa revealed that deworming has improved stunted growth, cognitive performance, and anemia level (Olds,2013). By reducing the pathogen load and disease burden of infectious diseases like worm infestation, diarrhea,

WASH (water, sanitation, and hygiene) intervention results in better nutritional status (Dodos, 2017). Interventions on water sanitation, hygiene, and actions on nutrition has shown positive nutritional outcomes (USAID, 2015, Tamiru, 2017).

United Nations Agency (UNICEF) in 2013 emphasized that community-based nutrition program for adolescents should be conducted, that include school based biannual deworming, behavioral change communication, promoting girl's education and also encourage nutrition, hygiene, and sanitation practices. In addition, the promotion of nutrition action through teachers, parent-teacher associations, and the incorporation of nutrition into the school's curriculum. Furthermore, the promotion of the use of iodized salt and micronutrient supplementation was recommended (Gilbert, 2013).

The results of the 13 randomized controlled trials based on multi-strategy intervention (including nutrition education and health of adolescents) from 2000 -2014 revealed that multi-strategy school-based nutrition programs resulted in good physical and mental growth of the adolescents when facilitated by teachers and parents, with adjustment in the school environment (Meiklejohn, 2016). Results of similar studies conducted in China revealed that a large number of students after nutrition education intervention in schools had better knowledge about the nutritional value of different food products than the control group (Wang, 2015). Another study finding showed that the prevalence of child malnutrition through planned nutrition education program in schools was reduced. The researcher found it a scientific, logical, and cost-effective strategy (Pateel, 2015).

Early adolescents (ages 10-14 years) are generally overlooked, as they are comparatively hard to reach, which in turn results to ignore the needs of adolescent girls and boys in this group. Early adolescents are a distinctive phase of life because it is a time of maximum physical and mental growth (Shahid, 2009). It was found that adolescent of this age group was not given due

importance and the focus remain on under five and lactating, pregnant women (LPW) age group. (Best 2010). The studies in Pakistan generally focused on physical status of children like weight and height in the age groups of 5-15 years. There is the poor outcome of nutritional status and WASH practices of early adolescent (10-14 years age) girls and boys, which formulates 12 % of the total population in Pakistan (Hirani, 2012 & NNS 2018).

Many researches and systematic reviews have been conducted in perspective of the nutritional status of under-five and lactating and pregnant adolescents by Aga Khan University Karachi (Bhutta, 2013,2016 & Salam,2016). However, very few researches have been conducted in Pakistan to assess the nutritional status of early adolescents (Fatime,2016 & Ahmed,2016, Ishaque, 2012). According to researcher knowledge, there is no study available on nutrition education with h integration of WASH components in early adolescents. The Government has ignored this fact usually, as there is a dire need to focus on the nutrition and WASH education of adolescent girls and boys through educational institutions in order to prevent future adverse outcomes (Fatima.2014). Therefore, the schools are the best setting to catchup this population and the implementation of the intervention strategies. In school-based health education, a conducive classroom environment plays an important role for adolescents to learn content and life skills. It also provides an opportunity for interactive discussions, to plan and practice community activities, and to reflect on those activities (Bhutta, 2015). Furthermore, school-going adolescents can also become a change agent for siblings, parents, and at community level. Studies have shown that the most common school health strategies for health education intervention focused on curriculum, school values, and beliefs, general environment, and focused on parent and community networks (Wang, 2013). The present study will focus on nutritional status with the integration of WASH practices of early adolescents. This study will be divided into three phases such as formative, RCT, and dissemination phase.

1. In the formative phase of the study focus group discussion with the early adolescents, their mothers/immediate caretakers, and school teachers to explore the perception regarding healthy diet and WASH practices. Key informant interviews will also be conducted with school management to explore the insight regarding enablers and barriers for the implementation of the school-based strategies.
2. In the RCT phase, baseline assessment of the school-going adolescents will be conducted (knowledge, attitude, and practices (KAP) regarding healthy diet and WASH practices, along with biochemical markers (Blood complete picture, Zinc, Calcium, and Vitamin D level) in subset of 180 participants from total adolescent's target study population. Furthermore, intervention focusing multi components strategies like nutrition education, deworming, Water, Sanitation, and Hygiene will be implemented for 6, 7, and 8 grade school going early adolescents. For the Adolescents mothers/Immediate care taker cooking recipe books will be provided in the local context based on Pakistan dietary guidelines. Workshop will be arranged for school teachers to train them as master trainer. In the end line of the study, KAP evaluation and biochemical, markers will be done to assess the effectiveness of the intervention.
3. Dissemination phase or research uptake

Pakistan has significantly high incidence of malnutrition, which needs to be explored and addressed in early adolescents. Poor nutritional status in children leads to lot of physical and mental problems during this phase of life and afterword. Healthy Nutrition result in better growth and development during this period and is a second window of opportunity for catch up growth who have already experienced stunting (Bundy,2018 & WHO,2014). According to Hossen, “well-nourished adolescents at present can make optimal use of their skills, talents, and energies and be healthy, responsible citizens and parents of healthy babies” (Bhutta,2014 & Hossen,

2016). Hence, for their physical and mental development a good nutrition has a major role to play (Bundy et al., 2018).

Therefore, this study is designed to assess the effect of Nutrition education and water, sanitation, and hygiene intervention on school going early adolescent girls and boys in Gojra, Pakistan and to suggest ways how to overcome this health issue.

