### **Study Setting**

For this study, public schools (boys and girls) in Gojra will be selected. There are 40 public schools (20 boys and 20 girls) in Gojra. We will invite the schools for study projects that fulfill the eligibility criteria (inclusion and exclusion criteria). From these willing schools, four public schools that are at least 1-2 Km away from each other (two boys and two girls) will be randomly selected via balloting. The inclusion criterion related to distance is intended to reduce contamination between schools of different arms. These four schools (boys and girls) will then be randomly assigned to either the school (one boy and one girl) with the intervention or to the school (one boy and one girl) without the intervention (Control school).

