### **Sample Size & Sampling Strategy**

The sample size was calculated by using PASS software. Sample sizes were estimated to change in nutritional status of early adolescent boys and girls. A sample size of 360 adolescents

(180 in each intervention and control group) will achieve 80% power assuming 42% malnutrition among students in the control arm and at least 6% reduction in the intervention arm having 90 students from each school at a two-sided 5% level of significance.

To assess the micronutrient levels (Iron, Zinc, Calcium, CBC, and Vitamin D) through a blood sample, a subset of 108 adolescents 6-8 grade school going adolescents (54 intervention group, 54 control group) from this total sample size (360) will be selected through random selection.

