### Data analysis plan

Quantitative variables will be described by means and standard deviations whereas median with interquartile range will be mentioned for qualitative variables. Frequencies and percentages will be calculated for the knowledge, attitude, and practices of adolescents regarding nutrition and WASH. The comparison between intervention and control at baseline and end line will be performed by using paired t-test and Chi-square. For the variables that are not normally distributed, a nonparametric test McNamara will be used. Binary logistic regression and multiple linear regression will be used to assess the effect of intervention. All the statistical analyses will be conducted using SPSS version 23. A p-value less than 0.05 will be considered statistically significant.

Descriptive	Inferential

 
• Mean, SD Normally distributed
 
• Median, interquartile range Skewed distribution
 
• Percentages and frequencies of knowledge, attitude, and practices
 
	
 
• Chi-Square-McNamara knowledge, attitude, and practices
 
• T- test paired Continuous variables
 
• Binary logistic regression and multiple linear regression
 
• Proportion changes - chi-square Observational checklist
 

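### Sex is an allocation stratum that the planned arm comparison does not carry, and a single malnutrition figure can let a fall in thinness and a rise in overweight offset each other

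*Protocol*

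**What the plan says.** **Sex and form of malnutrition.** The Introduction cites a national survey in which "boys are more affected than girls in terms of being underweight, and more adolescent girls are overweight compared to their male peers", and adds for the trial's province: "In Punjab province, more adolescent boys are underweight than girls". Both statements give a direction only; no sex-specific rates appear.

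**Allocation.** Study Setting draws two boys' and two girls' schools by ballot. It continues: "These four schools (boys and girls) will then be randomly assigned to either the school (one boy and one girl) with the intervention", with the other pair as controls. Single-gender schools are an eligibility requirement.

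**Outcome.** Hypothesis and Sample Size & Sampling Strategy (RCT phase) both refer to one prevalence of malnutrition, set at 42% in the control arm for both sexes together. The Introduction defines malnutrition as covering under- and overnutrition. The table of baseline activities counts thin, underweight, overweight and obese pupils. Expected outcome describes improvement as BMI rising to the normal range.

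**Analysis.** The RCT-phase Data analysis plan compares intervention and control by paired t-test and chi-square, and then states: "Binary logistic regression and multiple linear regression will be used to assess the effect of intervention". It names no stratum, covariate or sex-specific table.

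**The concern.** There are two linked problems.

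1. The allocation is balanced by sex, but the one test of proportions named for the arm comparison has no stratum. For the regressions the text neither includes nor excludes sex. A stratum that is used to allocate and then ignored leaves explainable variation in the error term.

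2. One combined malnutrition figure adds two conditions that an intervention expected to raise BMI could move in opposite directions. A modest net change could then hide a real gain in thinness together with a real harm in overweight. The Introduction suggests that these two burdens fall unevenly on boys and girls, so a breakdown by sex is useful description.

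**Working it through.** **Inputs from the protocol:** 42% control prevalence; a 6% reduction, read here as 6 points; 180 pupils per arm; 90 per school; two-sided 5%; a blood subset of 54 per arm. **Assumed, because the protocol gives no figures:** the boy-girl gap, the marker difference and the split between thinness and overweight.

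**The plan's own figure.** For 42% v 36%:

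n = [1.96 √(2 × 0.39 × 0.61) + 0.842 √(0.42 × 0.58 + 0.36 × 0.64)]² / 0.06² = 1037 per arm.

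With 180 per arm the power is about 21%, so the stated 80% does not reproduce. That is a separate matter, but it sets the base for what follows.

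**Precision lost on the binary outcome.** With equal numbers of boys and girls and a gap d in total prevalence, sex accounts for (d/2)² / (0.42 × 0.58) of the variance:
- d = 0: 0%
- d = 0.10: 0.0025 / 0.2436 = 1.0%
- d = 0.20: 0.0100 / 0.2436 = 4.1%

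Power for 42% v 36%, with no clustering, pooled against stratified:
- gap 5 points: 21.4% v 21.5%
- gap 10 points: 21.3% v 21.6%
- gap 20 points: 21.0% v 22.2%

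The gain is about 0.1 to 1.3 percentage points.

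**Precision lost on blood markers.** With equal sexes and a difference of k within-sex SDs, the removable share is (k/2)² / [1 + (k/2)²]:
- k = 0.5: 0.0625 / 1.0625 = 5.9%
- k = 1: 0.25 / 1.25 = 20%

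In pupils, 54 per arm analysed with sex is worth 54 × 1.0625 = 57 or 54 × 1.25 = 67.5 without it.

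**Cancellation in the combined figure.** Assume boys are 30% thin and 12% overweight, and girls 14% and 28%. Apply the same relative change to both sexes: thinness × 0.75 and overweight × 1.15.

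| | Before | After | Change (points) |
|---|---|---|---|
| Thin, both sexes | 22.0% | 16.5% | -5.5 |
| Overweight, both sexes | 20.0% | 23.0% | +3.0 |
| Combined, both sexes | 42.0% | 39.5% | -2.5 |
| Combined, boys | 42.0% | 22.5 + 13.8 = 36.3% | -5.7 |
| Combined, girls | 42.0% | 10.5 + 32.2 = 42.7% | +0.7 |

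The first two rows show the movement without any split by sex. The masking comes from adding the two conditions together. Pooling boys and girls is not its cause.

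**What a split by sex can establish.** Each sex has one school per arm. A model with arm, sex and their interaction fits four school means with four parameters, which leaves 4 - 4 = 0 degrees of freedom between schools. Even if there were no school effect at all, a 6-point effect in one sex only would have 12.8% power within that sex (90 v 90), and 8.4% in the pooled contrast, where it is halved to 3 points.

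**Cost in a school-level analysis.** Arm alone leaves 4 - 2 = 2 degrees of freedom (critical t 4.30). Adding sex leaves 4 - 3 = 1 (critical t 12.7).

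**The case against.** **Pooling is partly inferred.** The covariates of the regressions are open, and a SAP that is not shown could name sex. This stands for the regressions, where the fair statement is that the protocol does not commit to sex. It does not remove the point for the chi-square, which the protocol itself fixes without a stratum, or for the single combined prevalence.

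**The precision loss is negligible.** This stands for the binary outcome. The loss is zero if boys and girls have the same total prevalence, which is compatible with the Introduction because it describes different forms and gives no different totals.

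**The remedy can backfire.** In an analysis of four school means, the critical value rises 12.7 / 4.30 = 2.95-fold when sex is added. With no other school variance, removing a 10-point gap shrinks the expected standard error only about 1.7-fold; it takes a gap of about 20 points to break even. This stands, and limits the stratification advice to pupil-level comparisons unless the loss is accepted openly.

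**Readings that go too far.** A reader might infer that the boy-girl difference becomes between-school variance and overwhelms the effect. That would need an analysis that allows for school but not sex, and the protocol plans none. A reader might also infer that ignoring sex biases the result, but each arm has one school of each sex with 90 pupils per school. Finally, a reader might infer that a sex-stratified analysis would uncover an effect confined to one sex. It cannot, because sex-specific contrasts are fully confounded with school.

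**Conclusion.** The point holds in a limited form. The protocol allocates by sex and then names an arm comparison without that stratum. It also tests one malnutrition figure in which opposite movements of thinness and overweight can partly offset each other. The second element matters more for interpretation.

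For the binary outcome the precision at stake is 0 to about 4% of variance (gaps of up to 20 points). For blood markers it is about 6% to 20% (differences of 0.5 to 1 SD). The marker figures assume equal numbers of boys and girls in the subset, which the protocol does not guarantee. All these ranges rest on assumed sex differences.

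The cancellation argument assumes that the 42% includes overnutrition, as the Introduction's definition and the counted BMI classes suggest; the protocol gives no explicit binary definition. If only undernutrition is meant, a rise in overweight would fall outside the figure altogether, and separate reporting would still be needed. The two-schools-per-arm design, within-school correlation and the unsupported sample size are larger problems, and this point does not resolve them.

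**What to change.** In the RCT-phase Data analysis plan:

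1. Carry the allocation stratum into the between-arm comparisons: a sex-stratified prevalence difference (for example with a Cochran-Mantel-Haenszel test) in place of the plain chi-square, and sex as a fixed term in the logistic and linear models, including those for blood markers.
2. Beside the overall malnutrition result, report the arm difference for thinness and for overweight/obesity separately.
3. Add a breakdown by sex labelled descriptive, and state that no sex-specific effect will be claimed because each sex has one school per arm.
4. State that these steps do not deal with within-school correlation, which needs its own method. If that method is a school-level analysis of the four schools, acknowledge that the sex term uses one of the two degrees of freedom.

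The cost is wording and a few table rows. Sex is known from the school and the BMI classes are already recorded, so no new data are needed.
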